For all 97 treated patients, the median number of cycles administered was 3 (range, 1:17), the median duration of exposure was 13.1 weeks (range, 4:69), and the median relative dose intensity was 98.85%.

The ORR showed a dose response effect between the 3 mg/kg Q2W (ORR<10%) and doses of 10 mg/kg or higher (ORR  $\geq$ 20% in all arms). At doses of 10 mg/kg or higher, the response rate ranged from 20% to 29% without a meaningful dose response between the 10 mg/kg and the 20 mg/kg arms.

The median duration of responses were: 12.9 months (3.7-14.8) at 10 mg/kg Q2W; 9.2 months (3.7-13.8) at 10 mg/kg Q2W/Q4W; and 8.75 months (4.6-9.9) at 20 mg/kg QW/Q2W.

The response rates are consistent cross all sub-groups. In patients treated at doses  $\geq$ 10 mg/kg, ORR was  $\geq$ 20% in all sub-groups, including patients with high-risk cytogenetics (38% [8/21]).

The median PFS was: 3.7 months (1.84–10.15) across all dose levels. The median OS for 10 mg/kg Q2W group was 18.628 (9.9220 to NC) months, and has not been reached in the 10 mg/kg Q2W/Q4W and 20 mg/kg QW/Q2W arms.

Among the 97 patients enrolled, and across all the treatment cohorts, Grade  $\geq$ 3 TEAEs were reported in 63.9% of patients, serious TEAEs in 43.3%, TEAEs with fatal outcome in 10.3% (and 5 because of disease progression), and TEAEs leading to treatment discontinuation in 8.2% of the patients (2 due to infusion-related reactions, 1 due to Grade 3 thrombocytopenia, and 5 patients unrelated to toxicity). The most common TEAEs were nausea (35.1%; Grade 3-4, none), fatigue (30.9%; Grade 3-4, none), cough (28.9%; Grade 3-4 in 1%), and dyspnea (26.8%; Grade 3-4 in 3.1%).

Infusion-associated reactions were reported in 49 of 97 patients (50.5%) patients across all dose levels. The severity of the IARs was Grade 3 or higher in 3 (3.1%) patients. The symptoms of IARs with a severity of Grade 3-4 consisted of anaphylactic reaction, hypertension, dyspnea, bronchospasm (in 1 patient each).

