### AND

SGOT/AST and SGPT/ALT ≤ 4.0 x IULN

- d. Patients must have adequate renal function, as defined by:
  - Creatinine clearance (CrCl) ≥ 25 mL/min., as measured by a 24-hour urine collection or as estimated by the Cockcroft and Gault formula. The serum creatinine value used in the calculation must have been obtained within 28 days prior to registration. Estimated creatinine clearance =

(140 - age) x wt (kg) x 0.85 (if female) 72 creatinine (mg/dl)

- e. Patients must have bone marrow aspirate and biopsy within 35 days prior to registration. The following are required:
  - quantitative percent clonal plasma cell involvement,
  - standard immunophenotyping,
  - immunohistochemistry,
  - cytogenetics,
  - fluorescent in situ hybridization (FISH) (via participating site local laboratory) to assess for del 17p; t11;14; t4;14, t14;16; and del 13q.

Additionally, FISH and cytogenetic testing (normal – XY; and all abnormalities) are required to have been performed and to be reported, even if "no results" was achieved (i.e. due to too few cells in specimen). If FISH was performed, then the patient is eligible. If FISH was not performed, then patient is not eligible. Central pathology analysis will not be required, however the local pathology report and FISH/Cytogenetic data must be submitted in Medidata RAVE.

- f. Patients must have adequate bone marrow function as defined by the following within 28 days prior to registration: ANC  $\geq$  1,000 cells/mcl without growth factor support, AND platelets  $\geq$  75,000 cells/mcl.
- g. Patients must have hemoglobin  $\ge 8$  g/dL within 28 days prior to registration. Patients may have received transfusion if greater than 7 days prior to registration.
- h. Patients must have adequate cardiac function as defined by the following:
  - New York Heart Association (NYHA) < Class IV heart failure (see Section 18.2); and
  - $\overline{\text{LVEF}}$  by ECHO  $\geq$  35% within 28 days prior to registration; and
  - NT-proBNP ≤ 8500 pg/mL within 28 days prior to registration.
- i. Patients must have a Zubrod Performance Status  $\leq 2$ .
- j. Patients must not have any clinically significant uncontrolled systemic illness, including but not limited to uncontrolled, active infection requiring intravenous antibiotics, unstable angina pectoris, myocardial infarction within the past 6 months, uncontrolled cardiac arrhythmias, uncontrolled hypertension, or uncontrolled diabetes mellitus.

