## 8.5 Guidelines for the Management of Infusion Reactions (IRs)

Patients should routinely receive premedications prior to isatuximab infusion to reduce the risk and severity of IARs commonly observed with monoclonal antibodies. Infusion associated reactions are defined as AEs related to isatuximab with onset typically within 24 hours from the start of the infusion.

Patients presenting Grade 2 IAR(s) with infusion interruption may subsequently resume isatuximab at half of the initial infusion rate under close monitoring and supportive care as needed. These patients must be informed of the potential risk of recurrent infusion reactions upon rechallenge. For further infusions, patients may receive additional premedication per the judgment of the Investigator. Additional recommended premedications include diphenhydramine 25 mg IV (or equivalent) and methylprednisolone 100 mg IV.

Once a Grade 2 IAR leading to interruption has improved to Grade  $\leq 1$ , the infusion may be restarted at half the original infusion rate. If symptoms do not recur after 30 minutes, the infusion rate may be increased in 50 mg/hour increments every 30 minutes, to a maximum of 400 mg/hour.

Patients presenting Grade 3 or 4 isatuximab IAR(s) must have isatuximab permanently discontinued and appropriate supportive therapy should be administered. The IAR(s) and the therapy administered must be documented in the eCRF.

CTCAE Version 5.0 criteria definition	Intervention recommendation		
Mild (Grade 1) Infusion interruption or intervention not indicated	Continuation of isatuximab infusion per the judgment of the Investigator following close direct monitoring of the patient's clinical status. Isatuximab infusion may be stopped at any time if deemed necessary. If stopped, IAR will be classified as Grade 2 as per CTCAE Version 5.0.		
Moderate (Grade 2) Therapy or infusion interruption indicated, but responds promptly to symptomatic treatment (eg, antihistamines, NSAIDs, narcotics, IV fluids); prophylactic medications indicated for ≤ 24 hours	Stop isatuximab infusion. Give additional premedication with diphenhydramine 25 mg IV (or equivalent) and/or methylprednisolone 100 mg IV (or equivalent) as needed. Isatuximab may be resumed only after patient recovery, with slower infusion rate and with close monitoring.		

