#### 11.5 Safety Analysis

There is no formal Data and Safety Monitoring Committee for this study. Accrual reports are generated weekly and study-specific accrual is monitored by the Study Chair, Study Statistician and the Disease Committee Chair.

There will be a run-in to ensure safety of this treatment combination. Ten patients will initially be treated. The following adverse events of special interest are specified as a potential safety concern, if a patient experiences one of them in the 1st cycle of treatment. If two or fewer patients experience any of the toxicities listed below during the first cycle of treatment, then accrual will continue as planned. If three or more patients experience at least one of these toxicities during the first cycle of treatment, the trial will be temporarily closed to accrual pending a decision as to whether to continue accrual. If accrual is reopened, a protocol revision will include justification for continued accrual and for any treatment regimen modifications. If accrual is proceeding quickly, enrollment will be paused until all ten patients in the initial safety cohort have completed one cycle of treatment or experienced one of the events listed below.

Events to be monitored during safety run-in:

- Grade 3 and 4 infusion-associated reaction (IARs) defined as anaphylactic reaction, hypertension, or dyspnea.
- Grade 4 cardiac event (including CHF and arrhythmias) (or > 2 NYHA grades higher than patient baseline)
- Grade 4 neutropenia or thrombocytopenia that does not resolve to < Grade 3 within 10 days
- Grade 4 infection.
- Grade 4 gastrointestinal ileus, or obstruction.
- Grade 4 LFT abnormalities (AST, ALT, Bilirubin)

Reports summarizing adverse events, serious adverse events (SAEs) and treatment administration are provided monthly to the Study Chair and Study Statistician for monitoring. In addition, all SAEs, which by definition require expeditious reporting, are reviewed and processed by the Adverse Event Coordinator at the SWOG Operations Office and a physician reviewer based on data provided via the NCI CTEP-AERS system. Cumulative study-specific SAE reports are provided to the Study Chair and Study Statistician upon occurrence of an event. Formal reports summarizing the study are prepared for all SWOG members every 6 months.

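### The run-in counts only three presentations of Grade 3-4 infusion reaction, against the protocol's own wider definition, and adds a NYHA limb that few admitted patients can meet

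*Combined protocol and SAP*

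**What the plan says.** Section 11.5 sets up a safety run-in: "Ten patients will initially be treated". It then closes accrual temporarily under this condition: "If three or more patients experience at least one of these toxicities during the first cycle of treatment". With two or fewer such patients, accrual goes on. If accrual is fast, enrollment also waits until each of the ten has either finished a cycle or had a listed event.

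Two of the six listed items matter here.

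- **Infusion reactions:** "Grade 3 and 4 infusion-associated reaction (IARs) defined as anaphylactic reaction, hypertension, or dyspnea".
- **Cardiac:** "Grade 4 cardiac event (including CHF and arrhythmias) (or > 2 NYHA grades higher than patient baseline".

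Elsewhere the protocol treats infusion reactions more broadly. Section 8.5 states: "Infusion associated reactions are defined as AEs related to isatuximab with onset typically within 24 hours from the start of the infusion". Section 16.1f repeats that definition and asks for expedited reporting of IARs of Grade 3 or higher. Section 8.5 also requires permanent discontinuation after any Grade 3 or 4 IAR, whatever its symptoms.

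Section 2.4, on Phase II Stage 1 of TED10893, records Grade 3 or higher IARs in 3 of 97 patients and adds: "The symptoms of IARs with a severity of Grade 3-4 consisted of anaphylactic reaction, hypertension, dyspnea, bronchospasm (in 1 patient each".

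For cardiac function, Section 5.3h admits "New York Heart Association (NYHA) < Class IV heart failure". Appendix 18.1 gives classes I to IV, while Section 10.3d refers to a class 0 that the appendix does not contain.

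**The concern.** The run-in list names the first three of the four severe presentations in Section 2.4, in the same order, and leaves out the fourth without giving a reason. It introduces the three as a definition, not as examples. A run-in patient taken off drug for Grade 3 bronchospasm alone, or for any other unlisted severe IAR, would therefore not count toward three of ten. Section 7.1a says IARs occur most often at the first administration, so such a case would fall inside the run-in window.

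That patient has also neither completed a cycle nor had a listed event. The condition for lifting an enrollment pause does not say what to do with such a patient.

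The NYHA alternative has a separate problem: the required rise is larger than most admitted baseline classes leave room for.

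What is at stake is the trigger itself. Section 11.5 states that there is no formal data and safety monitoring committee, and this rule is the one place in the plan where a toxicity count closes accrual automatically.

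**Working it through.** **1. The plan's own figure.** Section 2.4 gives Grade 3 or higher IARs in 3 of 97 patients: 3/97 = 0.0309, the stated 3.1%. The plan states no operating characteristic for the run-in rule, so there is none to reproduce.

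**2. How many historical patients would the list miss?** Four symptoms, one patient each, occurred among three patients, so one patient had two of them. If the bronchospasm patient also had a listed symptom, the list misses 0 of 3. If not, it misses 1 of 3. The counted rate is therefore between 2/97 and 3/97. Bronchospasm is one quarter of the symptoms, but as a share of patients the figure is zero or one third.

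**3. Chance of a pause from IARs alone.** With X the number of counted patients among ten and p the rate of counted events,

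P(X ≥ 3) = 1 − Σ (k = 0 to 2) C(10, k) p^k (1 − p)^(10 − k).

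At p = 3/97: 1 − (0.7304 + 0.2331 + 0.0335) = 0.0030. At p = 2/97 the result is 0.0009.

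For higher rates, the true rate and the unlisted share are assumptions. The counted rate is the true rate × (1 − unlisted share). For example, 0.30 × 0.75 = 0.225.

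| Assumed true Grade 3-4 IAR rate | All counted | One quarter unlisted | One third unlisted |
|---|---|---|---|
| 10% | 0.070 | 0.034 | 0.025 |
| 20% | 0.322 | 0.180 | 0.139 |
| 30% | 0.617 | 0.398 | 0.322 |
| 40% | 0.833 | 0.617 | 0.524 |

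These figures treat IARs as the only trigger. The other listed events count toward the same three patients, so these are not the operating characteristics of the full rule.

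**4. Reach of the NYHA limb.** The wording is "or > 2 NYHA grades higher than patient baseline". Class IV is the top of the Appendix 18.1 scale.

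| Baseline class | Steps available to IV | Can rise by more than 2? | Can rise by at least 2? |
|---|---|---|---|
| I | 3 | yes | yes |
| II | 2 | no | yes |
| III | 1 | no | no |

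Of the three admitted classes, one can meet the limb as printed and two can if it means at least 2. If the class 0 of Section 10.3d is taken literally, patients in that class could meet it too. On no reading can a class III patient meet it.

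**The case against.** The strongest objection is size. Severe IARs were rare with this drug: 2.2% in the Phase I part and 3.1% in Phase II Stage 1. Rates of 30% to 40% are roughly ten times higher and come from no source in the documents. At the documented rate the wording changes the pause probability by at most about 0.2 percentage points, and possibly not at all. This stands. What it leaves is that a run-in exists to catch an unexpectedly high rate, and there the lost sensitivity is not small.

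A reader might infer that the cardiac item is blind in patients with the worst baseline heart function. The documents do not support this. The NYHA rise is an alternative to a Grade 4 cardiac event, and a Grade 4 event counts from any class. A class II or III patient who worsens to class IV is missed only if the event is not also graded 4. The printed sign may also have lost an equals bar when the PDF was read; that would add class II but not class III.

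A reader might also infer that several treatment-ending reactions could pass unnoticed. They would not. Grade 3 or higher IARs are reported as expedited, serious events have physician review, and the Study Chair and Study Statistician receive cumulative reports when an event occurs as well as monthly summaries. These give sight of the events but do not close accrual automatically.

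Finally, the gap in the pause condition errs toward caution, because enrollment would stay paused. It applies only if accrual is fast, and Section 11.1 expects 1 to 2 patients a month. It is an ambiguity, not a route by which an unsafe regimen passes. Nor does the point need the Section 2.2 statement that this is the first CD38 antibody study in AL amyloidosis, since Section 2.5 itself cites daratumumab experience in the disease.

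**Conclusion.** The point holds as a conflict between the run-in rule and the rest of the protocol. Followed literally, Section 11.5 does not count some reactions that Section 8.5 treats as severe enough to end treatment, and it does not say how such a patient affects release of a pause. The NYHA limb is near-empty, but it is not the only cardiac route.

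The numerical effect is negligible at the documented rate (0.30% against 0.09% at most). It becomes material only if severe IARs are far more common here: at an assumed 30%, the chance of a pause from IARs falls from 62% to 40% if a quarter are unlisted, and to 32% if a third are. Both the rate and the shares are assumptions, and the historical data are also compatible with no loss. What is lost is the automatic accrual trigger, not knowledge of the events. The correction is worth making because the stated rule departs from the protocol's own definition and is cheap to align.

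**What to change.** In Section 11.5:

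- Reconcile the IAR item with Sections 8.5 and 16.1f, so that Grade 3-4 IARs count by the protocol's own definition and not by a symptom list.
- State that a run-in patient permanently discontinued for such an IAR counts as having had an event when deciding whether a pause can be lifted.
- Reconcile the NYHA wording with Sections 5.3h and 10.3d and Appendix 18.1: one scale, and an explicit statement of which baseline classes can meet the criterion. The threshold is for the sponsor to choose.

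The cost is a few lines of text. The IARs are already collected and reported as expedited, and Section 9.0 already schedules NYHA assessment each cycle, so no new data are needed. The downside is a slightly higher chance of a temporary accrual pause: from IARs alone, at most about 0.2 percentage points at the documented rate, and more if severe reactions prove common. Nothing in patient care changes.

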#### 11.0 STATISTICAL CONSIDERATIONS

11.1 Two-Stage Design

The primary goal of this study is to test the hypothesis that the rate of confirmed overall hematologic response (CR+VGPR+PR) to treatment is at most 10% versus the alternative that the true hematologic response rate is 30% or greater.

A two-stage design will be used for patient accrual, with a total of 35 eligible patients who are evaluable for hematologic response per the definition in Section 11.2b below. (24) Patients who received at least one dose of study drug will be considered evaluable. Initially, 20 eligible, evaluable patients will be accrued. If one or fewer hematologic partial or better responses are observed in the first 20 patients, this treatment will be considered insufficiently active in this population and further accrual will be terminated. If two or more confirmed, partial or better responses are observed, then an additional 15 eligible, evaluable patients will be accrued. If at least 8 out of the total 35 patients have a confirmed response, the treatment may be recommended for further testing in subsequent studies. An estimated 39 patients will be enrolled to this study (including 35 eligible and evaluable patients, with 20 enrolled to Stage 1 and 15 enrolled to Stage 2, and with an additional 4 patients enrolled overall to account for ineligible and unevaluable patients).

With an estimated accrual rate of 1-2 patients per month, it is anticipated that the study will reach full accrual in 20 to 40 months.

- 11.2 Sample size and Power Justification
  - a. Assuming the number of hematologic responses is binomially distributed this design has a significance level of 2% and a power of 87% for detecting a true overall hematologic response rate of at least 30% versus the null hypothesis response rate of 10% of less.
  - b. All eligible patients who receive any study treatment will be considered to be evaluable for response and toxicity, and will be included in the analysis.
  - c. Patients who go off study or die prior to the first response assessment will be considered as non-responders.
- 11.3 Analysis of Primary Endpoint

The primary endpoint of this study is overall confirmed hematologic response rate (ORR), which includes partial response (PR), very good partial response (VGPR) and complete response (CR) as defined in Section 10.2.

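### Read literally, the Section 11.5 run-in list stops at Grade 4, so a fatal Cycle 1 event of a listed type with no earlier listed-grade event does not count toward the 3-of-10 accrual trigger

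*Combined protocol and SAP*

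**What the plan says.** Section 11.5 sets a safety run-in of ten patients. The continue rule is "If two or fewer patients experience any of the toxicities listed below during the first cycle of treatment, then accrual will continue as planned". The closure rule begins "If three or more patients experience at least one of these toxicities during the first cycle of treatment" and leads to a temporary closure to accrual pending a decision. If accrual is quick, enrollment pauses until "all ten patients in the initial safety cohort have completed one cycle of treatment or experienced one of the events listed below".

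Six event types are listed. The infusion reaction item reads "Grade 3 and 4 infusion-associated reaction (IARs) defined as anaphylactic reaction, hypertension, or dyspnea". The cardiac item reads "Grade 4 cardiac event (including CHF and arrhythmias) (or > 2 NYHA grades higher than patient baseline", where the bracketed NYHA clause is an alternative way to qualify. The other four (persistent neutropenia or thrombocytopenia, infection, ileus or obstruction, liver function tests) are each set at Grade 4. No item uses an open-ended grade, and none mentions Grade 5, a fatal outcome or death.

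On oversight, the same section states: "There is no formal Data and Safety Monitoring Committee for this study". It also states: "Cumulative study-specific SAE reports are provided to the Study Chair and Study Statistician upon occurrence of an event".

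For efficacy, Section 11.2c says how early deaths are handled: "Patients who go off study or die prior to the first response assessment will be considered as non-responders". Section 11.5 has no matching sentence for the run-in count.

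**The concern.** The 3-of-10 rule is the only numeric toxicity rule on accrual. Followed word for word, it counts a life-threatening infection or cardiac event but not a fatal one, unless the patient first had an event at a listed grade or met the NYHA clause. Two listed Grade 4 events plus one such death would read as 2 of 10, and accrual would go on. Three such deaths and nothing else would read as 0 of 10.

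The pause wording has the same gap, in the conservative direction. A patient who dies this way has neither completed the cycle nor had a listed event, so the release condition is never met for that patient.

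What is at stake is whether a temporary closure follows automatically or depends on interpretation when the count is one short. The gap matters mainly for infusion reactions, cardiac events, infection, and ileus or obstruction, where the listed event can itself be fatal.

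**Working it through.** **Plan figures.** The documents state no operating characteristics for the run-in, so there is none to reproduce. For context, the exact two-stage binomial (20 then 15 patients, stop at 1 or fewer responses, success at 8 or more of 35) gives alpha 0.0199 and power 0.866, in line with the 2% and 87% in Section 11.2a. The run-in count does not enter that calculation.

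**Grade wording compared.**
- Section 11.5: Grade 4, or Grades 3 and 4 for infusion reactions.
- Section 16.1, Table 16.1: a Grade 3-5 column. Its footnote on late events names Grade 5 separately from Grades 3 and 4.
- Section 16.1f, item 2: infusion reactions at Grade 3 or above, followed by a second bullet closed at Grade 3 or 4.
- Section 8.3, Table 1: the last row for each toxicity is Grade 4.

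So Grade 5 is named as its own grade elsewhere, but closed ranges are also common. The text does not settle what was meant in 11.5, and no other section adds deaths to the run-in count.

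**Effect of one uncounted death.** Inputs from Section 11.5: ten patients, trigger at three. Assumption: one patient has died of a listed type with no earlier listed-grade event, and the other nine have listed events independently at a common rate p. The documents do not give p, so 10%, 20% and 30% are shown. With X ~ Binomial(9, p):
- P(X=0) = (1−p)^9
- P(X=1) = 9p(1−p)^8
- P(X=2) = 36p²(1−p)^7
- Closure if the death counts: P(X≥2) = 1 − P(0) − P(1)
- Closure as written: P(X≥3) = P(X≥2) − P(2)

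| p | P(0) | P(1) | P(2) | Death counted, P(X≥2) | As written, P(X≥3) |
|---|---|---|---|---|---|
| 10% | 0.387 | 0.387 | 0.172 | 0.225 | 0.053 |
| 20% | 0.134 | 0.302 | 0.302 | 0.564 | 0.262 |
| 30% | 0.040 | 0.156 | 0.267 | 0.804 | 0.537 |

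The two readings differ only when exactly two of the other nine have a listed event, which is the P(2) column: 17%, 30% and 27%.

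**NYHA limb (secondary).** Section 5.3h requires a baseline class below IV, and the scale in Section 18.1 runs from I to IV. The largest possible rises are IV − I = 3, IV − II = 2 and IV − III = 1. A rise of more than two therefore cannot occur from Class II or III. If the symbol was meant as two or more, Class II could meet it but Class III still could not. The Grade 4 cardiac limb covers these patients either way. Section 10.3d also refers to a class 0, which Section 18.1 does not list.

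**The case against.** The strongest reply is that no study team would score a fatal infection as no event in a run-in meant to ensure safety. The protocol often stops at Grade 4 as shorthand, as in Table 1 and Section 8.5. Deaths are handled elsewhere: 24-hour expedited reporting, physician review, and cumulative reports to the Study Chair and Study Statistician, who also monitor accrual. Nothing says that accrual can close only through the 3-of-10 rule, and the closure is temporary. This largely stands. It makes loose wording the likely explanation and limits the weight of the point. It does not supply an accrual rule for the reporting route, and it leaves the count to interpretation where a numeric rule was meant to remove it.

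The affected case is narrow: a Cycle 1 death, of a listed type, with no earlier listed-grade event, and decisive only at the margin. That also stands. The percentages above are conditional on such a death and use assumed rates. The only comparable rates in Section 2.4 are for infusion reactions alone (2.2% at Grade 3-4 in Phase I, 3.1% at Grade 3 or higher in Phase II Stage 1), so nothing there supports the upper assumed values.

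The pause gap applies only if accrual is quick, and one to two patients per month are expected. It would equally affect a Cycle 1 dropout or a death of an unlisted type, which the change proposed here does not resolve.

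A reader might infer that deaths go unmonitored or were deliberately excluded. The documents do not support that, given the reporting routes above and the mixed use of open and closed grade ranges. A reader might also infer that every fatal listed event escapes the count. It does not: a patient who first has a listed-grade event is counted.

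**Conclusion.** The point holds as a wording gap in a safety rule. Taken literally, 11.5 leaves one kind of Cycle 1 death out of its only numeric accrual trigger and out of the pause release condition. If one such death occurs, the chance of temporary closure is 5%, 26% and 54% as written, against 23%, 56% and 80% if it counts, at assumed rates of 10%, 20% and 30% in the other nine patients. How often such a death would occur cannot be derived from the documents.

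It is tempting to borrow the fatal event rates in Section 2.4 (2.2% and 10.3%) to estimate an overall loss of closure probability. The documents do not support that. Those rates cover whole exposure and any event type, mainly in myeloma, may include deaths from progression, and do not show how many of those patients had an earlier listed-grade event.

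The NYHA point is secondary. Because Sections 10.3d and 18.1 disagree on whether a class 0 exists, no firm count of the baseline classes that can reach the limb should be drawn. Alpha, power and endpoints are unaffected. The change is worth making because it is cheap and concerns the most severe outcome of the listed events.

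**What to change.** In Section 11.5, state that fatal (Grade 5) events of the listed types count toward the 3-of-10 trigger and satisfy the enrollment-pause condition, consistent with the open-ended grade wording in Section 16.1. In practice the items would read Grade 4 or higher, and Grade 3 or higher for infusion reactions.

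Secondarily, the study team should check the symbol in the NYHA clause and reconcile Sections 5.3h, 10.3d, 11.5 and 18.1 on the classes in use.

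The cost is a few words in one section plus the NYHA reconciliation, with no added patients or assessments. The downside is a slightly higher chance of a temporary closure.
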